8 STUDY DESIGN

8.1 Overview of Study Design

This is a Phase 2, randomized, double-blind, placebo- and TEZ/IVA-controlled, parallel-group, multicenter study designed to evaluate the safety and efficacy of VX-440 in [REDACTED] triple combination with TEZ and IVA.

Approximately 198 subjects with CF will be enrolled across Parts 1 [REDACTED]. Enrollment of Parts 1 [REDACTED] will be sequential, while enrollment of Part 2 will be in parallel with Part 1 Cohort 1B. [REDACTED]

Part 1 will consist of 2 cohorts: Cohort 1A and Cohort 1B. The start of dosing of Cohort 1A and Cohort 1B will be sequential. After all Cohort 1A subjects complete the Day 15 Visit, a blinded review of all available safety and PK data will be conducted by the Vertex study team and lead investigator(s). Dosing of Cohort 1B will begin after the blinded review, if supported by safety and PK data.

Part 2 will initiate after the Cohort 1A blinded review, if supported by safety and PK data.

[REDACTED]

Key study elements of each part are summarized in Table 8-1. The treatment arms and randomization ratios for each part are summarized in Table 8-2. A schematic of the study design is shown in Figure 8-1 (Parts 1 and 2) [REDACTED]

Interim analyses are described in Section 12.3.6.1.

All parts of this study will include a Screening Period, Treatment Period, and Safety Follow-up Visit. Part 2 will also include a 4-week Run-in Period and a 4-week Washout Period after the Treatment Period.

Table 8-1 Key Study Elements by Part

	Part 1 ^a	Part 2
Genotype	F508del/MF	F508del/F508del
Age	≥18 years	≥18 years
ppFEV ₁ criteria	≥40 to ≤90	≥40 to ≤90
Number of subjects	Approximately 42 ^a	Approximately 24
Stratification ^c	ppFEV ₁ ^d • ≥70 • <70	ppFEV ₁ • ≥70 • <70
Study design	Parallel	Parallel
Comparator	Placebo	TEZ/IVA
VX-440 treatment duration	4 weeks	4 weeks

IVA: ivacaftor; MF: minimal function; ppFEV₁: percent predicted forced expiratory volume in 1 second; q12h: every 12 hours; TC: triple combination; TEZ: tezacaftor

[figure not shown]
^a Part 1 consists of Cohort 1A and Cohort 1B. Approximately 10 subjects will be in Cohort 1A and approximately 32 subjects will be in Cohort 1B [REDACTED]

^c Additional stratification information is provided in Section 8.1.3.

^d Stratification will be conducted for Cohort 1B subjects only.

Table 8-2 Treatment Arms and Planned Doses by Part

Part	Treatment Arm	VX-440 Dosage	TEZ Dosage	IVA Dosage

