12.3 Statistical Analysis

This section presents a summary of the planned statistical analyses of the primary PD and efficacy endpoints of the study. Statistical analysis details will be provided in the statistical analysis plan (SAP) and clinical pharmacologic analysis details will be provided in the clinical pharmacology analysis plan (CPAP). Both plans will be finalized before the clinical data lock and unblinding of the study.

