12.3.4.1 Pharmacodynamic Effect

The absolute change in sweat chloride from baseline through Day 29 is a secondary endpoint used to evaluate the PD objective of the study. The test to detect a decreasing dose-response trend of VX-440 at 2 doses in TC with TEZ/IVA relative to placebo based on sweat chloride, will be performed using the MCP procedure with the prespecified comparisons (contrasts) of the treatment group means within a linear MMRM framework. The model will include treatment group, visit, and treatment-by-visit interaction as fixed effects, with the ppFEV₁ stratification factor at randomization as a categorical covariate. The test will be performed using the 1-sided maximum *t*-statistic of the individual *t*-statistics for the multiple prespecified contrasts at alpha = 5%, based on the treatment group means through Day 29 in Cohort 1B.

[REDACTED]

Adjusted means and 95% confidence intervals of the average treatment effects through Day 29 or Week 12, as applicable, with 2-sided *P* values, for all within-group and between-group

comparisons in all parts will be estimated within MMRM, with appropriate adjustment for covariates.

Additional details of the analysis will be provided in the SAP.

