## 8.2.2 Demographics and Baseline Characteristics

Demographics, medical history and baseline characteristics will be summarized based on the FAS, and presented by treatment group and overall, for each part and cohort, as applicable.

Demographic data will include the following:

- Age at baseline (in years)
- Sex (female and male)
- Ethnicity (Hispanic or Latino, not Hispanic or Latino, and not collected per local regulations)
- Race (White, Black or African American, Asian, American Indian or Alaska Native, Native Hawaiian or Other Pacific Islander, and Other)

Baseline characteristics will include the following:

- Weight (kg)
- Height (cm)
- BMI (kg/m^2)

Stratification categories will include the following:

- ppFEV1 at stratification (< 70 and ≥ 70)

For subjects who are naïve to TEZ/IVA treatment in Part 2, ppFEV1 at Day -14 will be used for stratification; otherwise, ppFEV1 at screening will be used for stratification.

Disease characteristics will include the following:

- ppFEV1 at baseline (<40, ≥ 40 to <70, ≥70 to ≤90, >90)
- ppFEV1 at baseline (continuous)
- Sweat Chloride at baseline (continuous)
- FEV1 (L) at baseline (continuous)
- CFQ-R Respiratory Symptoms domain at baseline (continuous)
- Prior use of dornase alfa before first dose of study drug (Yes, No)
- Prior use of inhaled antibiotic before first dose of study drug (Yes, No)
- Prior use of any bronchodilator before first dose of study drug (Yes, No)
- Prior use of any inhaled bronchodilator before first dose of study drug (Yes, No)
- Prior use of any inhaled hypertonic saline before first dose of study drug (Yes, No)
- Prior use of any inhaled corticosteroids before first dose of study drug (Yes, No)

- Colonization with *Pseudomonas aeruginosa* at baseline (Positive, Negative)

A summary of medical history will be provided by MedDRA system organ class (SOC) and preferred term (PT) for the FAS. In addition, the number of subjects reported to have had positive cultures for respiratory pathogens in 2 years prior to screening will be summarized for the FAS. Further, the CFTR genotype for each subject will be provided in an individual subject data listing.

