### **8.3 Efficacy Analysis**

All efficacy analyses described in this section will be based on the FAS, unless otherwise specified. TC groups with TEZ 100 mg qd (Cohort 1A) and 50 mg q12h (Cohort 1B) for the same dose of VX-440 will be pooled for the primary model-based analysis of all efficacy and pharmacodynamic (PD) variables in Part 1. [REDACTED]

Treatment groups TC-1A and TC-1B-low in Part 1 will be presented both pooled and separately, for descriptive analysis.

The placebo group will include subjects from all cohorts within a part, for all analyses. The analysis will include all available measurements through the last scheduled on-treatment visit including measurements after treatment discontinuation, per the visit windowing rules described in Appendix B. The post-dose measurements on the same day will not be used for any model-based analyses, but only reported in descriptive analyses.

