#### 8.3.5.1 Primary Analysis of the Dose Response trend of absolute change in sweat chloride from baseline through Day 29 (Part 1)

The null hypothesis to be tested is that the dose response of the mean absolute change from baseline through Day 29 for sweat chloride is not decreasing between placebo and the TC dose groups of Part 1, with TC-1A and TC-1B-low pooled. The test will be performed using the MCP procedure with the pre-specified contrasts provided in Section 6.2.2.1, within a linear MMRM framework using PROC GLIMMIX in SAS. The model will include treatment group, visit, and treatment-by-visit interaction as fixed effects, with continuous baseline sweat chloride as a covariate, and will include all data from all treatment groups and visits through Day 29 for analysis. The dose response test will be based on the 1-sided maximum  $t$ -statistic of the individual  $t$ -statistics for the multiple pre-specified contrasts at  $\alpha = 5\%$ , based on the treatment group means through Day 29 (Day 15 and Day 29 only), using an unstructured covariance structure for the within-subject errors. If the model estimation does not converge, a reduced compound symmetry covariance structure will be used instead.

The tabular presentation of results for the average treatment effect across visits, and the treatment effect by visit will be similar to the primary analysis of the primary efficacy variable for Parts 1 and 2. The corresponding  $p$ -value for the decreasing dose response trend will be provided.

In addition, descriptive analyses of the change from baseline will be performed for all treatment groups by post-baseline visit, with TC-1A and TC-1B-low presented both pooled and separately, for descriptive analysis.

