#### 2. Exclusion criteria:

- a) E4: History of hemolysis.
- b) E5: G6PD deficiency, defined as G6PD activity less than the lower limit of normal (LLN) or 70% of the mean of the LLN and the ULN, whichever is greater.
- c) E6: Any of the following abnormal laboratory values at screening:
  - Hemoglobin  $< 10$  g/dL
  - Total bilirubin  $\geq 2 \times$  ULN
  - Aspartate aminotransferase (AST), alanine aminotransferase (ALT), gamma-glutamyl transpeptidase (GGT), or alkaline phosphatase (ALP)  $\geq 3 \times$  ULN
  - Abnormal renal function defined as glomerular filtration rate  $\leq 50$  mL/min/1.73 m^2 (calculated by the Modification of Diet in Renal Disease Study Equation) for subjects  $\geq 18$  years of age and  $\leq 45$  mL/min/1.73 m^2

(calculated by the Counahan-Barratt equation) for subjects aged 12 to 17 years (inclusive)

- d) E10: A standard digital ECG demonstrating QTc >450 msec at screening. If QTc exceeds 450 msec for the screening ECG, the ECG should be repeated 2 more times during the Screening Period, and the subject will be excluded if the average of the 3 QTc values is >450 msec.
  - e) E11: History of solid organ or hematological transplantation.
  - f) E16: Use of restricted medications as defined in the clinical study protocol, within the specified window before the first dose of study drug (Day 1 in Parts 1 [REDACTED], Day -28 in Part 2).
  - g) E17: Pregnant or nursing females: Females of childbearing potential must have a negative pregnancy test at screening and Day 1.
3. Stratification error based on comparing the IWRS stratification with the clinical database:
- Age at Screening Visit (<18, ≥18 years) from IWRS versus age at screening visit in the clinical database
  - % predicted FEV1 at Stratification (<70, ≥70) from IWRS versus ppFEV1 at the screening visit or Day -14 (Part 2) of the Run-in Period from the clinical database

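### The Part 1 sweat-chloride dose-response model has no ppFEV1 term, although Cohort 1B is randomised within ppFEV1 category; adding one is a cheap, small safeguard

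*SAP*

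**What the plan says.** Protocol 12.3.4.1 runs the maximum-t dose-response test within an MMRM that carries the ppFEV1 "stratification factor at randomization as a categorical covariate". The test is "based on the treatment group means through Day 29 in Cohort 1B".

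SAP 8.3.5.1 sets up the same test, with the same contrasts, "with continuous baseline sweat chloride as a covariate". It lists no ppFEV1 term, and it pools TC-1A with TC-1B-low. SAP 8.3 extends the pooling to the controls: "The placebo group will include subjects from all cohorts within a part, for all analyses".

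On stratification, footnote d to Protocol Table 8-1 (Section 8.1) says: "Stratification will be conducted for Cohort 1B subjects only". For Part 1, SAP 8.2.2 takes the stratum from the screening value: ppFEV1 "at screening will be used for stratification".

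Elsewhere the SAP keeps ppFEV1 in view. Its primary ppFEV1 model (8.3.1.1.1) has continuous baseline ppFEV1, and its CFQ-R model (8.3.2.2) has continuous baseline ppFEV1 beside the CFQ-R baseline and sex.

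**The concern.** Cohort 1B is randomised within ppFEV1 category, so its arms are balanced on that factor by design. If the factor is related to the outcome, the real sampling error of the treatment contrasts is smaller than that of an unstratified trial. A model without the factor does not see this. It leaves the between-category variation in the residual and reports a standard error that is too wide.

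At stake is a little efficiency in the dose-response test. The error runs in the conservative direction. Adjusting for baseline sweat chloride is a sensible addition, but it does not require ppFEV1 to be left out.

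**Working it through.** **Inputs from the documents.** Cohort 1A has about 10 subjects at 4:1 (8 active, 2 placebo). Cohort 1B has about 32 at 2:1:1 (16 high, 8 low, 8 placebo). Pooled as in the SAP: placebo 8 + 2 = 10, low dose 8 + 8 = 16, high dose 16, total 42. SD of change 13 mmol/L, 1-sided 5% maximum-t test, three contrasts, and mean changes 0/-15/-20 in the linear row (Protocol 12.1.2.1, Tables 12-3 and 12-4; SAP 6.2.2.1).

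**Assumptions not in the documents.** Half of subjects in each ppFEV1 category; a gap g between categories in mean sweat-chloride change of 0, 5 or 8 mmol/L; a correlation r between baseline sweat chloride and change of 0 or 0.3; blocks of four in Cohort 1B. Total SD is held at 13. Each subject contributes one mean change, a simplification of the two-visit MMRM.

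**Step 1: reproduce the plan's power.** For contrast c, t = Σcᵢmᵢ / (s√(Σcᵢ²/nᵢ)). In Cohort 1B alone n = 8/8/16 (placebo/low/high), with 32 - 3 = 29 df and critical value 2.04. For the linear contrast at 0/-15/-20, the noncentrality is 20 / (13√(1/8 + 1/16)) = 20/5.63 = 3.55. Taking the maximum over the three contrasts gives power of 94.9%, 99.0% and 96.4% for the three profiles, against 95%, 99% and 96% in Table 12-4. The inputs are therefore those the plan used.

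**Step 2: expected size.** Two equal categories g apart contribute g²/4 to the variance of 13² = 169. The reported standard error without the factor, relative to that with it, is about √(169 / (169 - g²/4)):
- g = 5: √(169/162.75) = 1.019
- g = 8: √(169/153) = 1.051

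**Step 3: simulation on the SAP's pooled groups (10/16/16).** 200,000 runs per cell, Cohort 1B stratified, Cohort 1A not. Baseline only is the SAP model: 42 - 4 = 38 df, critical value 1.986. Both adds ppFEV1 category: 37 df, critical value 1.987. Power is for 0/-15/-20. Monte Carlo standard error is about 0.05 points for type I error and at most 0.04 for power.

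| r | g | Type I %, baseline only | Type I %, both | Power %, baseline only | Power %, both | Power change |
|---|---|---|---|---|---|---|
| 0 | 0 | 4.99 | 5.00 | 97.27 | 97.20 | -0.07 |
| 0 | 5 | 4.71 | 5.01 | 97.45 | 97.63 | +0.18 |
| 0 | 8 | 4.27 | 5.03 | 97.67 | 98.23 | +0.56 |
| 0.3 | 0 | 5.05 | 5.05 | 98.29 | 98.21 | -0.08 |
| 0.3 | 5 | 4.64 | 4.95 | 98.30 | 98.49 | +0.19 |
| 0.3 | 8 | 4.27 | 5.05 | 98.50 | 98.92 | +0.42 |

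The simulated standard errors for placebo against high dose agree with step 2. At r = 0 the ratios are 5.286/5.198 = 1.017 (g = 5) and 5.290/5.035 = 1.051 (g = 8). At r = 0.3 they are 5.039/4.944 = 1.019 and 5.046/4.778 = 1.056.

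**Step 4: the swap itself.** On the same pooled set, moving from stratum only to baseline only changes power by +0.7, +0.4 and +0.1 points at g = 0, 5 and 8 when r = 0.3, and by -0.2, -0.5 and -0.8 points when r = 0. The SAP's choice is not worse in general; it depends on r and g.

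**The case against.** The case for leaving the SAP alone is good, and much of it stands.

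- **There is a likely reason for the change.** The SAP pools Cohort 1A, which was not stratified. A stratum at randomisation does not exist for about 10 of the 42 subjects, so the protocol's term cannot be carried over unchanged. This stands, although the visible SAP does not give it as its reason. It explains why the stratum could not be used as written. It does not explain why ppFEV1 is absent in any form, since screening and baseline values exist for everyone.
- **The protocol leaves the detail to the SAP.** Protocol 12.3 opens: "This section presents a summary of the planned statistical analyses". The SAP is the operative plan. A reader might infer that two competing versions of the test are in force; the documents do not support that.
- **Text is redacted.** A redacted entry follows 8.3.5.1 in the SAP contents list, and there are redactions within 8.3.5. A rationale or a supportive analysis may be there, so the point concerns only the visible primary model.
- **The gain is not assured.** No document links ppFEV1 category to sweat-chloride change. With no link, adding the term costs a little. The simulation puts this below 0.1 points; a rougher approximation that ignores the balance built into Cohort 1B puts it at up to 0.3.
- **Validity is not in question.** A reader might infer that dropping a stratification factor inflates false positives. It does the opposite: type I error stays at or below about 5% in every cell.

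**Conclusion.** The SAP's test is valid, and baseline sweat chloride is a sound covariate. What remains is a small, conditional loss. If ppFEV1 category separates sweat-chloride change by 5 to 8 mmol/L, the standard error is about 2 to 6% too wide, type I error is about 4.3 to 4.7% instead of 5%, and power at the planned effects is 0.2 to 0.6 points lower. Power of the pooled test stays above 97% throughout, against the 95% stated for Cohort 1B alone. With no gap there is nothing to recover.

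The loss would matter more if the drug worked less well than planned. Under an assumed profile of 0/-9/-12, a separate run of 100,000 simulations per cell gave a gain from adding the term of about 1.1 points at a gap of 5 and 3.3 at a gap of 8, against a cost of 0.2 to 0.3 points at a gap of 0. Neither that profile nor the gaps come from the documents.

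Low severity: a cheap improvement, not a flaw that threatens the result.

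**What to change.** In SAP 8.3.5.1, keep continuous baseline sweat chloride and add ppFEV1 category (<70, ≥70) as a term defined for all pooled Part 1 subjects. Use the randomisation stratum for Cohort 1B and the category from screening ppFEV1 for Cohort 1A, because screening is the value that Part 1 stratification uses.

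An alternative is continuous baseline ppFEV1, following the pattern of SAP 8.3.2.2. It is defined in the same way for every subject, and it avoids screening spirometry, which may be pre- or post-bronchodilator. It was not simulated here.

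Either choice should be made before the SAP is finalised for the first interim data cut. Neither restores the protocol's Cohort 1B test, and neither needs to.

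The cost is one clause, one degree of freedom, and about 0.1 points of power at the planned effects if there is no association. No new data are needed: Cohort 1A has screening spirometry, and SAP Appendix D already plans a check for "Stratification error based on comparing the IWRS stratification with the clinical database".

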**8.3.5.3 Absolute Change in Sweat Chloride from Baseline through Day 29 (Parts 1 and 2)** 

**8.3.5.3.1 Parts 1 and 2**

The analysis of the absolute change in sweat chloride from baseline through Day 29 will be based on an MMRM model similar to the analysis of the primary efficacy variable in Part 1, with the continuous baseline sweat chloride as a covariate. The presentation of results will also be similar.

The adjusted mean (with 95% CI) obtained from the MMRM analysis at each post-baseline visit through Day 29 in the Treatment Period will be plotted by treatment group, for each part.

A waterfall plot showing the subject-level absolute change in sweat chloride at Day 29 will be presented, by treatment group. The plots will be based on the pooled treatment groups for Part 1.

In addition, for each part, descriptive analyses of the change from baseline will be performed for all treatment groups by post-baseline visit. Treatment groups TC-1A and TC-1B-low in Part 1 will be presented both pooled and separately, for descriptive analysis.

## 8.4 Safety Analysis

For Parts 1 [REDACTED] all safety analyses will be based on data from the TE Period for all subjects in the Safety Set. For Part 2, all safety analyses will be based on the TE Period for the Treatment Period for all subjects in the corresponding Safety Set for the Treatment Period.

The overall safety profile of study drug will be assessed in terms of the following safety and tolerability endpoints:

- Treatment-emergent adverse events (TEAEs)
- Clinical laboratory values (i.e., hematology, serum chemistry, coagulation, and urinalysis)
- ECGs
- Vital signs
- Pulse oximetry

All safety data will be summarized by treatment group and overall, for each part.

All safety data will be presented in individual subject data listings.

### 8.4.1 Adverse Events

For analysis purposes, AEs will be classified as pretreatment AEs, TEAEs, or post-treatment AEs, defined as follows:

For Parts 1 [REDACTED]

**Pretreatment AE:** any AE that started before the first dose date of study drug

**TEAE:** any AE that worsened (either in severity or seriousness) or that was newly developed at or after the first dose date of study drug through the end of the TE period

**Post-treatment AE:** any AE that worsened (either in severity or seriousness) or that was newly developed beyond the TE period

For Part 2:

**Pretreatment AE:** any AE that started before the first dose date of study drug

**TEAE during the Run-in Period:** any AE that worsened (either in severity or seriousness) or that was newly developed at or after the first dose date of study drug through the end of the TE period for the Run-in Period

**TEAE during the Treatment Period:** any AE that worsened (either in severity or seriousness) or that was newly developed at or after the first dose date of study drug through the end of the TE period for the Treatment Period

**Post-treatment AE:** any AE that worsened (either in severity or seriousness) or that was newly developed beyond the TE period

For AEs with completely missing or partially missing start dates, if there is no clear evidence that the AEs started before or after study treatment, the AEs will be classified as TEAEs.

Details for imputing missing or partial start dates of adverse events are described in Appendix H.

AE summary tables will be presented for TEAEs only, for the TE period, or accordingly, the TE Period for Treatment Period in Part 2, by treatment group and overall, for each part and cohort, as applicable, for the following:

- Number of TEAEs (total number of TEAEs only)
- Subjects with any TEAEs
- Subjects with TEAEs by Strongest Relationship
- Subjects with TEAEs by Maximum Severity
- Subjects with TEAEs Leading to Study Drug Discontinuation (Discontinuation of all study drug)
- Subjects with TEAEs Leading to Study Drug Interruption (Interruption of all study drug)
- Subjects with Serious TEAEs
- Subjects with TEAE Leading to Death

Summaries will be presented by MedDRA system organ class (SOC) and preferred term (PT) using frequency counts and percentages (i.e., number and percentage of subjects with an event). When summarizing the number and percentages of subjects, subjects with multiple occurrences of the same adverse event or a continuing adverse event will be counted once,

and only the maximum severity level will be presented in the severity summaries, and the strongest relationship level in the relationship summaries.

All AEs, including pre-treatment AEs, TEAEs for all applicable periods (Run-in, Treatment, Washout), and post-treatment AEs, will be presented in an individual subject data listing based on the All Subjects Set. Further, subjects who enrolled from Study 661-110 will be identified from the subject ID in the listing.

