AEs, medications ^y , treatments and procedures	Continuous from signing of the ICF through the Safety Follow-up Visit									

^s FSH will be measured for any suspected postmenopausal female subjects with at least 12 months of continuous spontaneous amenorrhea.

^t A single blood sample will be collected for the G6PD activity test

^v Blood samples will be collected for PK analysis of VX-440, TEZ, M1-TEZ, IVA, and M1-IVA. On Day 1, samples will be collected before dosing (0 hours) and at 1, 2, 4, and 6 hours after dosing (relative to morning dose). On Day 15, samples will be collected before dosing (0 hours) and at 1, 2, 4, 6, and 8 hours after dosing. On Day 29, a predose sample will be collected before the morning dose of study drug. At the Day 43 Visit, a single blood sample for PK analysis will be collected before the morning dose of TEZ/IVA. At the ETT Visit, a single blood sample for PK analysis will be collected.

^w The last dose of TEZ/ivacaftor will be the morning dose on Day 57.

^x The last dose of VX-440 or placebo will be the morning dose on Day 29.

^y Refer to [Section 9.4](#) for details.

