10 STUDY DRUG ADMINISTRATION AND MANAGEMENT

Study drug refers to VX-440, TEZ/IVA, TEZ, IVA, and their matching placebos.

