12.3.5.1 Adverse Events

For analysis purposes, AEs will be classified as pretreatment AEs, TEAEs, or post-treatment AEs, defined as follows:

- Pretreatment AE: any AE that started before the first dose of study drug
- TEAE: any AE that increased in severity or that was newly developed at or after the first dose of study drug through the end of the TE Period
- Post-treatment AE: any AE that increased in severity or that was newly developed beyond the TE Period

For AEs with missing or partial start dates, if there is no clear evidence that the AEs started before or after study drug treatment, then the AEs will be classified as TEAEs.

AE summary tables will be presented for TEAEs only, overall and by treatment group for each Part, and will include the following:

- All TEAEs
- TEAEs by strongest relationship
- TEAEs by maximum severity
- TEAEs leading to treatment discontinuation
- Serious TEAEs
- TEAEs leading to death
- Frequently reported TEAEs

Summaries will be presented by MedDRA system organ class and preferred term using frequency counts and percentages (i.e., number and percentage of subjects with an event). When summarizing the number and percentage of subjects with an event, subjects with multiple occurrences of the same AE or a continuing AE will be counted once, only the maximum severity level will be presented in the severity summaries, and the strongest relationship level in the relationship summaries. In addition, a listing containing individual subject level AE data for all deaths and other serious and significant AEs will be provided separately. All AEs, including pre- and post-treatment AEs, will be presented in individual subject data listings.

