## **8.2 Background Characteristics**

### **8.2.1 Subject Disposition**

For the Treatment Period in Part 1, Part 2, [REDACTED], subject disposition will be summarized as described below.

The number of subjects in the following categories will be summarized by treatment group and overall, for each part:

- All Subjects Set (randomized or dosed in the Treatment Period)
- Randomized
- Full Analysis Set (FAS)
- Safety Set (for Part 2, this is the Safety Set for the Treatment Period)

The number and percentage (based on FAS) of subjects in each of the following disposition categories will be summarized by treatment group and overall:

- Completed study drug treatment
- Prematurely discontinued treatment and the reason for discontinuation (i.e., discontinued all study drugs)
- Completed study (i.e., completed Safety Follow-up Visit or completed all study drugs and re-entered Study 661-110 without Safety Follow-up per protocol)
- Prematurely discontinued the study and the reason for discontinuation

For the Run-in Period in Part 2, a separate disposition table will be provided with the following categories:

- All Subjects Set (enrolled or dosed in the Run-in Period)
- Completed treatment in the Run-in Period (i.e., completed randomization)
- Prematurely discontinued treatment during the Run-in Period and the reason for treatment discontinuation (i.e., discontinued all study drugs in the Run-in Period)
- Prematurely discontinued the study during the Run-in Period and the reason for study discontinuation

A listing will be provided by part, for subjects who discontinued treatment (including the Run-in Period in Part 2) or who discontinued study with reasons for discontinuation. A randomization listing of subjects will also be provided, by part.

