#### **8.2.5 Study Drug Compliance**

Percentage of tablets taken will be calculated as:  $100 \times [(total\ number\ of\ tablets\ dispensed) - (total\ number\ of\ tablets\ returned)] / (total\ number\ of\ tablets\ planned\ to\ be\ taken\ per\ day \times duration\ of\ study\ drug\ exposure\ in\ days)$ . The maximum percentage of tablets taken will be 100%.

Study drug compliance will be calculated as:  $100 \times [1 - (total\ number\ of\ days\ of\ study\ drug\ interruption) / (duration\ of\ study\ drug\ exposure\ in\ days)]$ . A study drug interruption on a given day will be determined by an interruption of all drugs on that day.

Percentage of tablets taken and study drug compliance will be summarized descriptively by the number of subjects (n), mean, SD, SE, median, min, and max. It will also be summarized in categories:  $<80\%$  and  $\geq 80\%$  using frequency tables.

For all parts, study drug compliance will be summarized for the Treatment Period only. Similarly, for all parts, percentage of tablets taken will be summarized for the Treatment Period only.

Percentage of tablets taken and study drug compliance summaries will be based on the FAS, and presented by treatment group and overall, for each part.

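### The SAP counts a TEAE as leading to discontinuation or interruption only when all study drug is stopped, so in Part 2 a stop of VX-440/placebo alone would not appear in those summaries

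*SAP*

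**What the plan says.** The tolerability of VX-440 in combination is a primary objective (Protocol 6.1, SAP 4.1), and safety is analysed descriptively (Protocol synopsis).

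SAP 8.4.1 lists two relevant AE summaries: "Subjects with TEAEs Leading to Study Drug Discontinuation (Discontinuation of all study drug" and "Subjects with TEAEs Leading to Study Drug Interruption (Interruption of all study drug". SAP 8.2.1 defines the disposition category the same way: "Prematurely discontinued treatment and the reason for discontinuation (i.e., discontinued all study drugs". SAP 8.2.5 does so for interruption-based compliance: "A study drug interruption on a given day will be determined by an interruption of all drugs on that day".

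Protocol section 10 fixes the scope of the term: "Study drug refers to VX-440, TEZ/IVA, TEZ, IVA, and their matching placebos". The AE table list in Protocol 12.3.5.1 has the item "TEAEs leading to treatment discontinuation" with no all-drugs qualifier, and it has no interruption table.

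The two treatments end at different times in Part 2. Footnotes to Protocol Table 3-3 say "The last dose of VX-440 or placebo will be the morning dose on Day 29" and "The last dose of TEZ/ivacaftor will be the morning dose on Day 57". Protocol 10.6 describes VX-440, TEZ/IVA, TEZ and IVA as separate tablets, each with its own matching placebo.

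**The concern.** In a combination trial with active background therapy, the usual tolerability question is whether an adverse event led the subject to stop the drug under test. The SAP's rows answer a narrower question: whether it led the subject to stop everything. The two can differ in Part 2, because TEZ/IVA is given before, during and after VX-440.

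Compared with a count of stops of VX-440/placebo or any component, the all-drugs count can be equal or lower, never higher. Safety is read descriptively in small arms, so one or two missing subjects would visibly change the reported rate.

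**Working it through.** **1. Tracing one subject through the SAP.** Take a TC-2 subject who stops VX-440 on Day 10 for a TEAE and takes TEZ/IVA to Day 57.

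| SAP summary | What it shows |
|---|---|
| 8.4.1 TEAE leading to discontinuation | Not counted: not all study drug stopped |
| 8.4.1 TEAE leading to interruption | Not counted, for the same reason |
| 8.2.1 premature treatment discontinuation | Not counted |
| 8.2.5 interruption-based compliance | 100 × (1 − 0/29) = 100% |
| 8.2.4 exposure, Treatment plus Washout | 57 − 1 + 1 = 57 days, as for a completer |
| 8.2.4 exposure, overall (Day -28 to 57, no Day 0) | 28 + 57 = 85 days, as for a completer |
| 8.4.1 any TEAE, severity, relationship, serious (if applicable); AE listing | Event appears, but these tables do not show that VX-440 was stopped |
| 8.2.5 percentage of tablets taken | Falls (step 2) |

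For Part 2, SAP 8.2.4 reports exposure only for these two spans, regardless of interruption. No visible Part 2 summary gives the duration of VX-440 itself.

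**2. The two compliance measures, for a 14-day hold of VX-440 alone within 29 days.** The planned TC-2 doses (Protocol Table 8-2) and tablet strengths (Protocol 10.6) give:

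- VX-440 600 mg q12h: 3 × 2 = 6 tablets per day
- TEZ 50 mg q12h: 1 × 2 = 2
- IVA 300 mg q12h: 2 × 2 = 4
- Total: 12 active tablets per day, or 13 if one TEZ/IVA-matching placebo tablet is also taken (an assumption; the documents shown give no daily tablet count)

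With Day 29 treated as a full day, as the SAP formula does:

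- Tablets withheld: 14 × 6 = 84
- Percentage of tablets taken: 100 × (1 − 84/348) = 75.9% at 12 per day (29 × 12 = 348), and 100 × (1 − 84/377) = 77.7% at 13 per day (29 × 13 = 377)
- Interruption-based compliance under the SAP: 100 × (1 − 0/29) = 100%
- The same formula applied to VX-440 alone: 100 × (1 − 14/29) = 51.7%

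For the Day 10 stop, with about 19 days lost, 19 × 6 = 114 tablets. The percentage taken is 100 × (1 − 114/348) = 67.2% or 100 × (1 − 114/377) = 69.8%.

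If the high dose were reduced to 400 mg q12h (4 VX-440 tablets per day, 10 to 11 in total), the 14-day hold would give 100 × (1 − 56/290) = 80.7% to 100 × (1 − 56/319) = 82.4%.

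**3. Size per subject.** The planned Part 2 arms are 24 × 3/4 = 18 in TC-2 and 24 × 1/4 = 6 in TEZ/IVA. One uncounted subject is 1/18 = 5.6 percentage points in TC-2 and 1/6 = 16.7 points in the control arm.

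**4. Chance that the row shows anything (illustration).** SAP Table 6-3 uses the binomial model P(at least 1) = 1 − (1 − p)^n. It reproduces: n = 10 and p = 5% give 40.1% against the stated 40%; n = 40 and p = 10% give 98.5% against 98%. The documents give no rate of VX-440 stops for adverse events and no share that would be VX-440-only, so both are assumed here. For n = 18:

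| Assumed rate of VX-440 stops | All counted | Half are VX-440-only | All are VX-440-only |
|---|---|---|---|
| 5% | 60% | 37% | 0% |
| 10% | 85% | 60% | 0% |
| 15% | 95% | 75% | 0% |

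**The case against.** The strongest reply is that the protocol treats study drug as one unit. Section 10.4 interrupts, discontinues and resumes study drug as a whole, section 8.1.6 triggers the early termination visit on ending study drug treatment, and Table 13-3 records one action for study drug. No visible passage provides for stopping VX-440 alone or for moving early to the Washout regimen. In TC-2 the partner drugs are TEZ 50 mg q12h and IVA 300 mg q12h, and Protocol 8.2.2 explains that IVA dose by VX-440's induction effect. No arm gives that pair without VX-440. This stands as a reason to doubt that component-only stops would be common. It does not exclude them, because nothing forbids them. If none occur, the added rows equal the existing ones.

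The second reply is that the event is not lost. It enters the other AE tables and the listing. At the planned dose the 14-day hold also puts the subject in the below-80% category for tablets taken, which is a potential important protocol deviation under SAP 8.2.6 and Appendix D. This also stands, but that measure pools all tablets, is not linked to an adverse event, and would present the subject as non-compliant.

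Third, the protocol's AE item does not say any component, and Protocol 12.3 leaves details to the SAP. The SAP wording is a narrowing of an unspecific item, not a clear departure from it.

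A reader might also infer that the SAP classes such a subject as tolerating treatment, or that the all-drugs qualifiers prove partial stops were foreseen. The SAP has no tolerating category, and the qualifiers may only be a coding clarification.

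**Conclusion.** The point holds as a reporting gap in Part 2 that is cheap to close. Should a subject stop or hold VX-440/placebo for an adverse event while TEZ/IVA continues, the link between event and stop is absent from both TEAE rows, from premature discontinuation, from interruption-based compliance and from exposure. Its size is 5.6 percentage points per such subject in TC-2, given the planned 18. The total effect cannot be stated, because the frequency is unknown and could be zero.

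Three stronger readings are not supported:

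- **That it distorts dose selection.** The visible dose decision for TC-1B-high and TC-2 rests on Cohort 1A safety and PK data after a blinded review (Protocol 8.1 and Table 8-2). It is not tied to these rows, and the IDMC reviews safety separately.
- **That it is equally serious in Part 1.** Part 1 has no TEZ/IVA background, and Protocol 8.2.1 says no corrector/potentiator efficacy is established in that genotype, so the scenario has much weaker support there.
- **That it necessarily favours VX-440 over control.** The rule applies equally to matching placebo in the control arm. What follows is only that the count in either arm can be too low.

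**What to change.** - **SAP 8.4.1:** add rows for TEAEs leading to discontinuation, and to interruption, of VX-440/placebo or any study drug component. Keep the all-study-drug count as a sub-row.
- **SAP 8.2.1:** report premature discontinuation of VX-440/placebo, with reason.
- **SAP 8.2.5:** also report interruption-based compliance for VX-440/placebo.

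Use component-level dosing or action-taken data where the CRF records them. Table 13-3 suggests that action taken may be recorded once per event, so check the eCRF first. If it is recorded only once, the AE rows cannot be split on that field and would need dosing records.

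The cost is a few extra table rows and SAP wording, best settled before the data cut for the first interim analysis. Reported discontinuation and interruption rates can only stay the same or rise. The change concerns tabulation only and proposes no stopping rule.
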